- 1) Dial study phone number (from jabber or any phone)
- 2) Once voicemail starts, select *
- 3) Instruction's state: "Enter your ID followed by pound" enter phone number: **xxxxx#**
- 4) Instruction's state: "Enter your pin followed by pound" enter pin: **xxxxx#**

(Note: PIN #'s are required to be changed often, study staff will add a 1 to pin each time it needs to be updated.

PILOT STUDY FLOW CHART

PILOT RANDOMIZED IMPLEMENTATION TRIAL

TRIAL SITE SELECTION

- We will update national VA and Medicare data to identify eligible sites for the cRCT.
- All VA sites with high rates of low-value ADT from 2020 – 2022 will be considered eligible to participate in the study.
- We will start with the 40 facilities with the highest rates of low-value ADT and continue down the list as necessary.
- We will exclude sites requiring translated materials (e.g., Puerto Rico).
- If feasible, we will exclude sites scheduled to transition to Cerner prior to the end of the cRCT.
- We will randomize 4 VA facilities with high rates of low-value ADT use.

TRIAL SITE RECRUITMENT & RANDOMIZATION

- The top 4 sites with high rates of low-value ADT use and meeting above criteria will be invited to participate in the study.
- All invited sites that agree to participate will be included.
- We expect 80% participation by eligible sites.
- If sites are unwilling or unable to participate, we will continue down the list of sites until we reach a maximum of 4 participating sites.
- Study staff will send an email from the study Co-PI to Urology Chiefs to recruit as Site Champions.
 - If we are unable to contact Urology Chiefs, or if we do not receive a response from the Urology Chief after two formal email contacts, we may reach out to the Chief of Surgery, Chief of Med/Onc, or Chief of Rad/Onc (and copy the ACOS/R) about serving as Site Champion.
 - If the Urology Chief declines to serve as Site Champion, we may ask if they have any suggestions for an alternate designee.
 - In the event we are unable to recruit a Site Champion, all Site Champion communications will come from the study team.
- Once Site Champions have obtained approval from the MCD, each site will be randomized to the **Or** or **Sc** arm. The Data Manager will work with our Consultant, [name] on randomizing sites.

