 - Our current plan will be to stratify sites by availability of Radiation Oncology to ensure there is an even distribution of Radiation Oncology in both intervention arms. We intend to randomize sites in blocks of 2-4.
- Once site Clinical Health Information Officer has agreed to implementation the intervention at their site, study staff will apply for site CPRS access.
 - Note: Once you have CPRS access for a site, set an Outlook reminder to log in to each site every 30 days.

TRIAL OR/Sc IMPLEMENTATION

- Implementation procedures will be similar to those of the pilot but refined as needed based on pilot outcomes and needs specific to trial site implementation.
- Interventions will be implemented for up to 12 months at each site.
- Study staff will apply for CPRS access at each site once we receive approval from either the Medical Center Director or Site Champion.
- Baseline ADT Prescribing Meetings – these meetings with Site Champions or their designees will not be mandatory for the RCT. We will move forward with our trial implementation even if we haven't collected information regarding the ADT ordering process.

- Implementation Education Session (IES) – to make scheduling easier on the study team, we may implement one IES per site instead of each department. We will move forward with implementing the interventions after scheduled IES's, even if they have been cancelled.
- There is a possibility that patients will receive ADT injections more than once during the intervention period. If this is the case, then the intervention will be triggered more than once for the same patient.

TRIAL DATA COLLECTION

- Data sources for our primary, implementation and secondary fidelity outcomes will be refined during the pilot. Data collection and outcomes analyses plan will also be further developed during the pilot.
- We will likely assess **Or** fidelity using informatics data generated through the ordering process.
- We will use chart review to identify **Sc** documentation in the EMR, in addition to other informatics approaches.

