APPENDIX III: cRCT EMAIL TEMPLATES

cRCT Email Templates for Site Champions

- To MCD
- To Pharmacy Chief
- To Clinical Department Chiefs
- To Providers

cRCT Study Team Email Communications

- To Recruit Site Champion
- To Clinical Department Chiefs
 - a. Baseline ADT prescribing meeting
 - b. Confirm list of providers
- To CHIO/CACs
- To Site Champion/Department Chiefs to Schedule IES
- To Providers

Template Email to MCD from Site Champion

Cc: Site ACOS of Research

Attachments: AA IRB Exemption Approval Letter

Subject: <<Insert site name>> Participation in study, "Living Well with Prostate Cancer"

Dear <<Insert Medical Center Director name>>,

The purpose of this email is to request your support for participation in a research project funded by the NIH National Cancer Institute and coordinated by the VA Ann Arbor Healthcare System. The overall objective of this project, entitled "Living Well with Prostate Cancer", is to support decreased use of low-value Androgen Deprivation Therapy (ADT) in a way that is acceptable to the clinicians treating these patients. Low-value ADT (not supported by guidelines) includes primary treatment for localized prostate cancer and non-metastatic biochemically recurrent prostate cancer with low PSA levels. I will be acting as site champion, helping to support the Ann Arbor VA study team by getting them in touch with the appropriate clinic staff at our site.

The goal of this project is to test one of two tools to support providers in decreasing low-value care. Our participation will last for up to 12 months. At our site we will be testing <<insert for Or site: an ADT order-check (only triggered when orders meet criteria for low-value care.)>> or <<insert for SC site: a CPRS note template for clinic visits meeting criteria for low-value care. The note includes talking points for the provider to help with a de-implementation discussion with the Veteran. It can be edited and signed by the provider, giving a quick and simple way to document a discussion. Handouts for patients about ADT use will be supplied for providers to use at their discretion.>>

Testing these strategies will allow the study team to determine which strategy is most effective in reducing low-value ADT use.

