<< **Insert for Or site:** Attached is an example of how we have implemented this in Ann Arbor with an installation guide from our CAC. This can be completed within 15 minutes. To minimize the burden to providers, we only want the order check to be triggered for Veterans who are getting low-value ADT. We are also hoping you will set up a health factor for "LIVING WELL ADT". A member of the Ann Arbor project team with access to CPRS at your site will assign this health factor to Veterans meeting the criteria.>>

<< **Insert for Sc site:** Attached is an example of the progress note. >>

In addition to the staff mentioned above, we will also be working with <<insert name(s) of relevant department chiefs to make sure providers are educated about the study and the intervention.>> We would like to talk with you to see if the Ann Arbor example is a good way to accomplish our goals at your site, or if there is a different way that may better fit the current workflow at your site. We are also hoping to learn the following information:

- Are there currently any order checks/cover sheets/etc. for ordering ADT active at your site?
- <<insert for Sc site: Should we use current, past, or non-billable encounters to attach the progress note? Or should we create a current encounter?>>
- <<insert for Sc site: Is there a link to a progress note status report you can share?>>
- Is it reasonable for you to implement our intervention at your site?
 - If yes, how much notice do you need prior to the date we would like the new order check or note template to go live?
 - << **Insert for Or site:** The study team will need access to your site's CPRS to enter health factors. Can you let us know how to request CPRS access?
 - << **Insert for Sc site:** The study team will need access to your site's CPRS to assign progress notes to providers. Can you let us know how to request CPRS access?

If we can provide any additional information please let us know. If it is easier to talk by telephone please let us know a good time to contact you, or you can reach us at <<(XXX) XXX-XXXX>>.

Thank you, and we look forward to hearing back from you by <<date – ~1 week>> via telephone or email.

The Living Well with Prostate Cancer Study Team

XXXXXXX <<Insert team member name>>
XXXXXXX <<Insert team member name>>
XXXXXXX <<Insert team member name>>
Center for Clinical Management Research
VA Ann Arbor Healthcare System (152)
[contact]
(XXX) XXX-XXXX

Follow-up Email to CAC(s) from Study Team

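### The email asking a director to approve a site is written by arm, although approval must come before randomisation, so allocation is either unconcealed from the approver or the stated order cannot be followed

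*Protocol*

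**What the plan says.** The trial is small: "We will randomize 4 VA facilities with high rates of low-value ADT use" (Trial Site Selection). Trial Site Recruitment & Randomization then gives the steps in order.

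- Sites are invited from the top of a ranked list. The replacement rule reads: "If sites are unwilling or unable to participate, we will continue down the list of sites until we reach a maximum of 4 participating sites".
- Randomisation follows the director's approval: "Once Site Champions have obtained approval from the MCD, each site will be randomized".
- The next step listed concerns the informatics officer (CHIO): "Once site Clinical Health Information Officer has agreed to implementation the intervention at their site", staff apply for access to the site's records system (CPRS). A bullet in the following section, Trial Or/Sc Implementation, instead ties that application to approval by the director or the Site Champion.

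Appendix III holds the emails for these steps.

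- The trial email to the director opens: "The purpose of this email is to request your support for participation in a research project funded by the NIH National Cancer Institute". It then states what the site will do: "At our site we will be testing <<insert for Or site: an ADT order-check (only triggered when orders meet criteria for low-value care.)>>", with a separate insert for Sc sites. A later sentence is inserted for Sc sites only. The director is asked to confirm support or raise concerns.
- The email to the CHIO and clinical applications coordinators (CACs) also names the arm, and asks: "Is it reasonable for you to implement our intervention at your site".
- The email that recruits Site Champions is different. It says that sites will be randomised and describes both tools.

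**The concern.** In a cluster trial, randomisation protects the comparison of Or with Sc only if each site's decision to take part is made without knowing its arm, and if the site stays in the arm it drew. Site leaders here have reason to prefer one tool: Or interrupts ordering, while Sc supplies an optional note. The protocol itself lists, in Table D1.2, the possibility that willingness to take part varies with the preferred intervention.

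If the director approves, or the informatics officer agrees, knowing the arm, then the sites that make up each arm can depend on the arm. The leadership's readiness to restrict ADT would then be mixed with the effect of the tool. With so few sites, no adjustment could separate the two.

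**Working it through.** The protocol gives no figure of its own on this point, so the main check is a comparison of texts. The arithmetic only shows scale.

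**1. Director: stated order against the email**

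| Item | Place | Content |
|---|---|---|
| Order | Trial Site Recruitment & Randomization | Approval, then randomisation |
| Request for approval | Appendix III, trial email to the director | One tool inserted according to the site's arm, plus one sentence for Sc sites only |
| Mention of randomisation in that email | Same | None |
| Site Champion email | Appendix III | Both tools described, randomisation stated |

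The email needs the arm, and the arm does not exist until the email has been answered. Both cannot hold as written.

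**2. Informatics officer**

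The CHIO's agreement stands after the randomisation step. The email names the tool and asks whether implementing it is reasonable. The answer is therefore given with the arm known and can be negative. Nothing asks before the draw whether either tool could be installed. The two bullets on CPRS access give different conditions, so it is not settled whether the CHIO's agreement is required.

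**3. Replacement**

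The rule runs until four sites participate and states no end point. Its place, before the randomisation bullet, suggests that it serves recruitment. The text does not say that it stops there.

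**4. Scale**

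Inputs from the protocol: 4 sites, two arms, 80% expected participation by eligible sites.

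- Share of an arm changed by one loss or replacement, assuming a 2:2 split: 1/2 = 50%.
- Chance that the first four invited sites all accept: 0.8^4 = 0.41. Expected invitations: 4/0.8 = 5. So the replacement rule will probably be used at some stage. This says nothing about whether that happens after allocation.

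Assumption, not in the protocol: each site in an arm refuses after learning its arm with probability q, independently. The chance that at least one of two sites is lost is 1 − (1 − q)^2.

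| q | Calculation | Chance per arm |
|---|---|---|
| 0.05 | 1 − 0.95^2 | 0.0975, about 10% |
| 0.10 | 1 − 0.90^2 | 0.19 |
| 0.20 | 1 − 0.80^2 | 0.36 |

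**The case against.** The best defence of the director email is that it is only a template: it mentions two tools, and the inserts are joined by *or*, so both could be left in for every site. This does not stand. The inserts are labelled for one type of site each, and a later sentence is for Sc sites only.

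The objections to the later steps have more force.

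- **Replacement.** A reader might infer that an informatics refusal after the draw leads to the site being replaced. No passage says so. Read in sequence, the rule fills refused invitations. What stands against the plan is only that the end point is unstated.
- **Veto.** A reader might infer that the CHIO can block a site alone. The bullet tying CPRS access to the director or Site Champion contradicts that, and the email also invites adaptation to local workflow, so a doubtful answer need not mean that the site leaves.
- **Concealed losses.** A reader might infer that replacement would hide refusals. Table 4 counts site withdrawals as an implementation outcome, so losses would at least be visible. How withdrawn sites are analysed may be settled in a statistical analysis plan that is not at hand.
- **Unequal burden.** Or does need more services, but that remark explains the choice of pilot sites. The trial email to the CHIO puts the Or installation at 15 minutes, both tools are sent as files for local installation, and the pharmacy chief is only notified.

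None of these touches the conflict between the approval step and the approval email.

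**Conclusion.** The conflict over the director's approval is certain, because it rests on two explicit texts. As written, either the approver knows the arm or the planned order is not kept. The weakness at the informatics step is a gap: agreement is sought with the arm known, the condition for record access is stated in two ways, and replacement has no stated end. A site could therefore be lost knowing its arm. The protocol does not show that any was.

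The size is half an arm for each such loss, if the four sites split evenly. Its likelihood cannot be taken from the protocol. A reader might take the stated 80% participation to imply a 36% chance of a loss in the Or arm. That would move a general recruitment figure wholly to after the draw and onto one arm, which nothing in the text supports. The 10%, 19% and 36% above are illustrations under assumed refusal rates, and they are chances of a loss, not amounts of bias in the outcome.

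**What to change.** 1. **Director email.** Make it arm-neutral: describe both tools, say that the site will be randomised, and ask for agreement to whichever is drawn. The Site Champion email already has suitable wording.
2. **Informatics agreement.** Contact the CHIO and CACs before the draw, and randomise only when they agree that either tool can be installed. Reconcile the two conditions for CPRS access.
3. **After the draw.** State that replacement ends at randomisation. State too that a randomised site that declines or withdraws stays in its assigned arm, with outcomes from the Corporate Data Warehouse (CDW) and chart review at the trial's planned time points (baseline, 3 and 6 months, under Data collection), where record access allows. The control sites are not a full precedent, since they are reviewed only at intervention start and at the end of the 6 months.
4. **Sites already allocated.** The CPRS instructions for Sc already name two RCT sites to which notes are assigned, so items 1 and 2 may come too late for them. For every allocated site, report whether the arm was known when the director approved, and whether any site was replaced after allocation.

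The cost is one reworded email, one contact moved earlier, one rule added and a short report. There are two small downsides: sites that will not accept one of the tools are lost before randomisation, and a site that does not implement its tool dilutes its arm.

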We will administer a survey to assess feasibility and acceptability of the intervention, determine organizational structure and support, and assess fidelity in the interventions. We will work with study consultants throughout the pilot to further refine the survey, inviting the consultants/Site Champions at each of the 4 pilot sites to test the preliminary survey at baseline and 6 months in VA Qualtrics to understand how

best to use the survey in our cRCT. The purpose of piloting the survey with the consultants/Site Champions is to help inform further refinement of survey questions as well as implementation procedures in preparation for the cRCT. During the cRCT, selected providers and stakeholders at the 20 participating sites will be sent an email at baseline and 6 months inviting them to participate in the survey. The email will contain a link to an anonymous survey hosted in VA Qualtrics.

C2.0. Broad intervention categories require tailored design: Formulary restriction & decision-making

There are several potential implementation interventions to de-implement low value castration within each broad intervention category we identified for this study. We focus on an order check and physician communications during the informed decision-making because of their difference in key attributes, including likelihood of quick success vs. long-term sustainment and effort required by clinicians. We describe some possible intervention design features briefly for each intervention type in Table 2. While several options exist, there is no existing evidence to inform which is the best approach from the provider perspective. Our early work has informed which of these specific approaches is likely to be most acceptable to clinicians, and provided data needed to tailor these broad interventions. For example, we do not know how a blunt formulary restriction can be implemented at a national level. Nuances around order restriction need to be addressed and order checks programmed to only trigger when a patient meets certain criteria based on their medical record data without burdening providers with additional steps even when prescribing ADT within guidelines.

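### With four sites, stratifying by Radiation Oncology in blocks of 2 to 4 guarantees neither an even Radiation Oncology distribution nor two sites per arm

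*Protocol*

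**What the plan says.** Trial Site Selection sets the number of clusters: "We will randomize 4 VA facilities with high rates of low-value ADT use". Trial Site Recruitment & Randomization makes four a ceiling as well: if an invited site declines, "we will continue down the list of sites until we reach a maximum of 4 participating sites". The mix of sites with and without Radiation Oncology is therefore not known until recruitment ends.

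The same section ties allocation to local approval: "Once Site Champions have obtained approval from the MCD, each site will be randomized to the" Or or Sc arm. It then plans to "stratify sites by availability of Radiation Oncology to ensure there is an even distribution of Radiation Oncology in both intervention arms", followed by "We intend to randomize sites in blocks of 2-4".

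Two other places bear on the point:
- C1.0 Study population still speaks of "selected providers and stakeholders at the 20 participating sites", and the trial's provider information email in Appendix III gives about the same number.
- The instructions for assigning a progress note in the Sc intervention name two trial sites, Columbia and Phoenix.

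**The concern.** Stratified permuted blocks balance arms when strata hold enough sites to complete the blocks. At about 20 sites that is workable. At four, a stratum may hold one, two or three sites, and a block of 4 started there is never finished. An odd-sized stratum cannot be split evenly by any method. A block of 3, which falls within the stated range, cannot be 1:1 at all.

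Two things are at stake:
- **Arm sizes.** A 3:1 result leaves one arm as a single site. Strategy and site are then indistinguishable in that arm, and between-site variation there cannot be seen. If both arms have the same between-site variance, the between-site part of the variance of the arm difference is proportional to 1/3 + 1 = 4/3, against 1/2 + 1/2 = 1 for a 2:2 split. That is one third larger.
- **Radiation Oncology balance.** Table 4 compares adoption and penetration across medical oncology, radiation oncology and urology, so an arm without Radiation Oncology would weaken one of the trial's own outcomes.

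**Working it through.** The Protocol gives no balance probability to reproduce, so the possible allocations are enumerated exactly.

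**Inputs from the Protocol.** Four sites; two strata (Radiation Oncology available or not); block sizes within 2 to 4.

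**Assumptions.** Allocation is 1:1, as two arms and an even distribution imply. Each stratum has its own permuted-block list, and its sites take the first places on that list. The number of sites with Radiation Oncology is not given, so every split is considered. Three readings of the block size are used: always 2, always 4, or 2 and 4 chosen with equal chance.

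**2+2 strata.** Let p be the chance that a two-site stratum splits 1:1. Each of the two lopsided results then has chance (1 − p)/2.
- Blocks of 2: p = 1.
- Blocks of 4: of the 6 orderings of AABB, 4 begin with one A and one B, so p = 4/6 = 2/3.
- Equal mix: p = 1/2 × 1 + 1/2 × 2/3 = 5/6.

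The arms are 2:2 if both strata split evenly or if they are lopsided in opposite directions:

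P(2:2) = p² + 2 × [(1 − p)/2]²

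- Blocks of 4: 4/9 + 2 × (1/6)² = 4/9 + 1/18 = 1/2.
- Equal mix: 25/36 + 2 × (1/12)² = 25/36 + 1/72 = 17/24 = 0.71.

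P(3:1) = 2p(1 − p), which is 4/9 and 5/18 respectively. P(4:0) = 2 × [(1 − p)/2]², which is 1/18 and 1/72.

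**3+1 strata.** The first three places of AABB, or a full block of 2 plus one further site, always give 2:1. The lone site in the other stratum is a coin toss: it joins the smaller side (2:2) or the larger side (3:1), each with probability 1/2, whatever the block size.

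**4+0 strata.** A fixed block size of 2 or 4 always gives 2:2. With the equal mix, balance can fail only when a block of 2 is followed by a block of 4 (probability 1/4): P(2:2) = 1/2 + 1/4 + 1/4 × 2/3 = 11/12.

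| Strata | Blocks | P(2:2) | P(3:1) | P(4:0) | P(Radiation Oncology sites split evenly) |
|---|---|---|---|---|---|
| 2+2 | 2 | 1 | 0 | 0 | 1 |
| 2+2 | mix of 2 and 4 | 17/24 | 5/18 | 1/72 | 5/6 |
| 2+2 | 4 | 1/2 | 4/9 | 1/18 | 2/3 |
| 3+1 or 1+3 | any | 1/2 | 1/2 | 0 | 0 |
| 4+0 (all with Radiation Oncology) | 2 or 4, fixed | 1 | 0 | 0 | 1 |
| 4+0 (all with Radiation Oncology) | mix of 2 and 4 | 11/12 | 1/12 | 0 | 11/12 |

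**Comparison: one restricted draw.** There are 6 ways to put four sites into arms of two. With a 2+2 mix, 4 of the 6 split Radiation Oncology 1:1, and a draw among those 4 guarantees both properties. With a 3+1 mix, all 6 leave a one-site difference in Radiation Oncology, the smallest possible, and all 6 give 2:2.

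**The case against.** The strongest reply is that the scheme can work and probably did.

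- **Favourable cases exist.** With 2+2 strata and blocks of 2, or one stratum and a fixed block size, balance is perfect. A reader might infer from the 0.50 figures that the scheme must fail, or fails half the time. The Protocol does not support that: it fixes neither the block size nor the stratum split, and the full range for P(2:2) is 0.50 to 1.00.
- **Sequential allocation is not stated.** A reader might infer that sites are allocated singly, so that with blocks of 2 the second allocation in a stratum is known in advance. The text makes approval a precondition for each site, which suggests that order but does not settle it. Blocks could also mean batches of sites, and one batch of all four treated as a single block gives 2:2. Predictability is thus only a conditional worry, and inviting sites by rank on low-value ADT rate leaves little room to exploit it.
- **A 2:2 result has probably occurred.** Two Sc sites are named among four randomised. A reader might infer that the trial ran with a one-site arm; nothing in the Protocol indicates this.
- **The wording is provisional** ("Our current plan will be to stratify sites by availability of Radiation Oncology"), and exact block sizes are often kept out of a protocol. This is also a four-cluster pilot with matched control sites, where site and strategy are hard to separate even at 2:2.

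These replies limit the consequence. They leave the central point standing: the Protocol claims a property that the scheme has only under conditions it does not impose, and batching does not rescue the 3+1 mix. A 2:2 outcome does not show that the scheme guaranteed it, and the Radiation Oncology balance obtained is not reported.

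**Conclusion.** The point holds as a fault in the stated design property. For four sites the scheme does not ensure an even Radiation Oncology distribution and does not guarantee two sites per arm. How far it falls short depends on facts not given: P(2:2) is 1.00, 0.71 or 0.50 for 2+2 strata according to block use, and 0.50 for 3+1 strata with any block size, where an even Radiation Oncology split cannot be had by any method. The figures assume 1:1 allocation and a separate block list in each stratum. That the arms were in fact unequal, or that allocations were predictable in practice, does not follow from the Protocol.

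**What to change.** If allocation is still open, wait until all four sites have approval. Then randomise them in one draw restricted to 2:2 allocations with the best attainable Radiation Oncology balance: 1:1 if the mix is 2+2, and an unavoidable one-site difference if it is 3+1. Matching sites into two like pairs would not cover the 3+1 mix, where one pair must be unlike; the restricted draw covers every mix. Replace the promise to ensure an even distribution with a statement that Radiation Oncology is balanced as far as possible, and remove the block range.

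If allocation is done, state the method actually used, the arm sizes, and the Radiation Oncology distribution obtained.

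The cost is a few lines of protocol text and, in the first case, a short wait for the sites approved first.
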